 8.6.4 Physical examinations 25

8.7 Interim analysis.....	25
9 CHANGES TO PLANNED ANALYSIS FROM STUDY PROTOCOL.....	26
10 REFERENCES.....	27
11 APPENDICES.....	28

LIST OF ABBREVIATIONS

Abbreviation or special term	Explanation
AE	Adverse Event
ADR	Adverse Drug Reaction
BMI	Body Mass Index
CI	Confidence Interval
CRF	Case Report Form
CSR	Clinical Study Report
eCRF	electronic Case Report Form
EOS	End of Study
GI	Gastrointestinal
ICF	Informed Consent Form
ICH	International Conference on Harmonization
IWRS	Interactive Web Response System
MedDRA	Medical Dictionary for Regulatory Activities
mITT	Modified Intent to Treat
PP	Per-Protocol
PT	Preferred Term
RLD	reference listed drug
SAE	Serious adverse event
SAP	Statistical Analysis Plan
SOC	System Organ Class
TD	Travelers' Diarrhea
TEAE	Treatment-Emergent Adverse Events

TOC	Test of cure
USA	United States of America
WHO	World Health Organization

1 INTRODUCTION

The purpose of this Statistical Analysis Plan (SAP) is to provide detailed descriptions of the safety data derivations and data displays for study protocol 1526 RIF_2, Version 2.0, titled “A randomized, double-blind, parallel group, placebo-controlled, multi-center, therapeutic equivalence study to compare Rifaximin 200 mg tablets (Sandoz GmbH) to Xifaxan® 200 mg tablets (Salix Pharmaceuticals, Inc.) and placebo in patients with travelers’ diarrhea” dated 29 Oct 2015 for Final analysis. The SAP was prepared by [REDACTED] Biostatistics and Programming Department, specifically drafted by [REDACTED] [REDACTED] reviewed by [REDACTED] and [REDACTED]. Final analyses will be executed by [REDACTED].

[REDACTED]. The last patient last visit was on April 23rd, 2017. The final analysis, which will include only safety analysis due to low number of randomized patients, will be scheduled after the last patient has completed the 30 day safety follow up, and the resulting clinical database has been cleaned, quality-checked and locked.

The table of contents and templates for the TFLs will be produced in a separate document.

Any deviations from this SAP will be described and justified in the Clinical Study Report (CSR).

The preparation of this SAP has been based on International Conference on Harmonisation (ICH) guidelines^{1,2}.

All data analyses and generation of TFLs will be performed using SAS 9.3® or higher.

2 STUDY OBJECTIVES

2.1 Primary objectives

The primary objective of this study is to demonstrate the therapeutic equivalence of Rifaximin 200 mg tablets to Xifaxan 200 mg tablets in patients with travelers' diarrhea (TD). In addition, the efficacy of Rifaximin and Xifaxan will be compared to Placebo to assess the assay sensitivity of the study.

2.2 Secondary objective

The secondary objective of this study is to compare the safety and tolerability of Rifaximin 200 mg tablets to Xifaxan 200 mg tablets and to Placebo in patients with TD.

3 STUDY DESIGN

3.1 General study design

This study is a randomized, double-blind, parallel group, placebo-controlled, multi-center therapeutic equivalence study to compare Rifaximin 200 mg tablets to Xifaxan 200 mg tablets and placebo in patients with TD.

The reference listed drug (RLD) in this study is the rifaximin 200 mg tablet marketed in United States of America (USA) by Salix Pharmaceuticals, Inc. under the trade name Xifaxan®. The investigational product produced by Sandoz GmbH also contains 200 mg of rifaximin.

Patients will undergo screening procedures at the study site and eligible patients will be randomized to one of the study treatments. Treatments administered (randomized in 2:2:1 ratio) are:

- Rifaximin 200 mg tablets
- Xifaxan 200 mg tablets
- Placebo tablets

The first dose will be self-administered immediately following randomization, thus initiating Study Day 1. Subsequent doses will be taken approximately once every 8 hours for 72 hours for a total of 9 doses. Study Day 1 will begin with the first administration of study drug and Study Day 2 will begin 24 hours after the first treatment. Study Day 3 will begin 48 hours after the first treatment. Depending on the timing of the first administration of study drug on Visit 1, a Study Day may extend across 2 calendar days. Thus, the final dose(s) of study drug taken on Study Day 3 may actually be taken on the 4th calendar day of the study.

[figure not shown]
Patients will be contacted by telephone on Study Day 3 to determine if their condition has improved. Patients will return to the study site on Study Day 5 (\pm 1 day) for the test of cure (TOC)/End of Study (EOS) visit. Patients will participate in the study for a maximum of 7 calendar days.

Patients will maintain an electronic Patient Diary daily for recording the date, time and form of all stools passed; the time and date of study drug administration; the presence or absence and severity of signs and symptoms of enteric infection; body temperature; and presence or absence of blood in the stool.

The use of any concomitant medications and the occurrence of any AEs will be recorded on a paper Supplemental Form.

A schematic presentation of study design is as shown in Figure 1.

Figure 1: Study Flow Chart

AE=adverse event; EOS=end of study; TOC=test of cure

1. At Visit 1 (Study Day 0) patients will undergo screening and randomization and then eligible patients will self-administer their first tablet (initiating Study Day 1).
2. Depending on the timing of the first dose, and given the window of ± 1 day for the TOC/EOS Visit, the TOC/EOS Visit can take place anywhere from Calendar Day 4 to Calendar Day 7.
3. Study Days are measured in 24 hour periods, starting with the first dose of study drug. Depending on the timing of the first dose, 1 Study Day may extend across 2 calendar days.
4. One tablet of the randomized treatment approximately every 8 hours, for a total dose of 9 tablets.
5. Stool sample for diagnosis and culture; pre-enrollment stool form and frequency; physical examination; vital signs; clinical laboratory tests; urine pregnancy test (if appropriate); distribution and instructions on use of thermometer, electronic Patient Diary and paper Supplemental Form for documentation of concomitant medications and AEs.
6. Stool sample for diagnosis and culture; physical examination; vital signs; clinical laboratory tests; urine pregnancy test (if appropriate); AE and concomitant medication assessment. Collection of Patient Diary.

3.2 Randomization, blinding and unblinding

At each study center, patients who are eligible to enter the double-blind treatment period will be randomized to generic Rifaximin 200 mg, Xifaxan 200 mg or matching Placebo according to a 2:2:1 randomization ratio through an Interactive Web Response System (IWRS).

The staff at the study center, the Sponsor and its representatives, and all patients will be blinded to the identity of the investigational product.

3.2.1 Procedure for Breaking the Randomization Code

The treatment code may be broken for an individual patient in the case of an emergency and when the knowledge of the investigational product is essential for the clinical management of the safety of this patient. The Investigator must make every effort to contact the Medical Monitor before breaking the treatment code. The Investigator will be able to access the IWRS database to receive the treatment code, 24 hours a day and 7 days a week. A record will be kept at each study center of all broken treatment codes, of the person who broke the treatment code, date, time and of the reasons for breaking the treatment code. In the case of a code break, the Investigator must inform the Sponsor or its representative immediately, without revealing to the Sponsor or its representative personnel the result of the code break.

The Sponsor will have a designated Safety Manager at the Central Case Processing Site that has access to the randomization codes via the IWRS who may unblind a case if it is deemed medically appropriate.

3.3 Study treatments and assessments

The duration of participation for a patient is a maximum of 7 calendar days, including a maximum of 4 calendar days of treatment with study drug (depending on the number of doses taken on Calendar Day 1).

A detailed description of study procedures and assessments to be conducted during the study is provided in the protocol and summarized in the Schedule of Study Schedule/Flowchart in Table 1 below.

Table 1: Schedule of Study Assessments

Procedure	Study Day 0* Screening/ Randomization	Study Day 1*	Study Day 2	Study Day 3	Study Day 4	Study Day 5* (± 1 day) TOC/EOS	Day 30 (± 7 days) Follow-up Phone Call
Informed Consent ¹	X						
Eligibility Verification	X						
Medical History, Demographics	X						
Physical Examination ²	X					X	
Vital Signs ³	X					X	
Clinical Laboratory Tests ⁴	X					X	
Signs and Symptom Assessment of TD	X					X	
Stool Culture/Fecal Leukocytes ⁵	X					X	
Urine Pregnancy Test ⁶	X					X	
Randomization, Study Drug Dispensing	X						
Study Drug Administration ⁷		X	X	X			
Completion of Electronic Patient Diary ⁸		X	X	X	X	X	
Telephone Call to Patient				X ⁹			
Concomitant Medication Use ¹⁰	X	X	X	X	X	X	
Adverse Event Assessment ¹⁰	X	X	X	X	X	X	X ¹¹
Review of Diary/Supplemental Form				X		X	
Drug Accountability and Compliance						X	

AE=Adverse Event; EOS=End of Study; ICF=Informed Consent Form; TD=travelers' diarrhea; TOC=test of cure

* Screening/Randomization (Study Day 0) and Study Day 1 are the same day. Study days are 24 hour periods. Study Day 1 will begin with the administration of the first dose of study drug, Study Day 2 will begin 24 hours after the administration of the first dose of study drug, and so on. Depending on the timing of the first dose of study drug, one Study Day may extend over two calendar days. Depending on the timing of the first dose, and given the window of ± 1 day for the TOC/EOS Visit, the TOC/EOS Visit can take place anywhere from Calendar Day 4 to Calendar Day 7.

1 Informed consent must be obtained before the patient undergoes any study-specific procedures. The Investigator must confirm that the patient is able to read and understand the language of the ICF, Patient Information, the electronic Patient Diary, and the Supplemental Form.

2 Weight and height will be measured at Screening; weight will be measured at the TOC/EOS visit. Body mass index (BMI) will be calculated at Screening and TOC/EOS.

3 Vital signs (respiratory rate, heart rate, blood pressure, and body temperature) will be performed at Screening and the TOC/EOS Visit. They will be obtained in the sitting position after the patient has rested for 5 minutes. The date and time of the assessment should be recorded.

4 To include hematology, clinical chemistry and urinalysis.

5 A stool sample will be obtained for fecal leukocyte testing and culture prior to randomization to study drug and on TOC/EOS. Stool culture for pathogenic organisms including: Enterotoxigenic *Escherichia coli* (ETEC); Enteroaggregative *E. coli* (EAEC); *Shigella* spp; *Salmonella* spp; *Campylobacter jejuni*; *Plesiomonas* spp; *Aeromonas* spp; Rotavirus; *Giardia lamblia*; *Entamoeba histolytica*, *Cryptosporidium* spp.

6 For female patients of childbearing potential (not post-menopausal or have not undergone surgical sterilization), the results of the urine pregnancy test must be negative to confirm eligibility prior to randomization.

7 The first dose of study drug is considered to be on Day 1, and is to be taken as soon as possible following completion of the Screening/Randomization procedures. The remaining 8 doses are to be taken at even intervals for 3 doses per day – a total of 9 doses of study drug are to be taken.

8 At Screening/Randomization, the patient will be given an electronic Patient Diary in which to record his/her symptoms; time of study drug administration; and date, time and form of all stools passed. The Patient Diary will be reviewed by the Investigator during the call on Study Day 3 at the TOC/EOS Visit.

9 Site will contact patient on Study Day 3 to check on their clinical status (i.e., if their condition has improved) and review completion of Diary and Supplemental Form. Information on AEs and concomitant medication will also be collected.

10 Patients will be given a paper Supplemental Form for documentation of the administration of any concomitant medications or the occurrence of any AEs. The Form will be reviewed by the Investigator during the call on Study Day 3 and at the TOC/EOS Visit.

11 A follow-up phone call is to be performed should the patient have any ongoing AE at the TOC/EOS Visit. Any ongoing related AEs will be followed until resolution or until assessed by the Investigator to be permanent.

4 STUDY ENDPOINTS

4.1 Primary efficacy endpoints

The primary endpoint of this study is clinical cure at the TOC/EOS Visit (Study Day 5 \pm 1 day). Clinical cure is defined as either:

- no stools or only formed stools within a 48 hour period and no fever, with or without other enteric symptoms, OR
- no watery stools or no more than two soft stools passed within a 24 hour period with no fever and no other enteric symptoms except for mild excess gas/flatulence

4.2 Secondary efficacy endpoints

Following are the secondary endpoints in this study:

- Time to Last Unformed Stool (TLUS) defined as the interval beginning with the first dose of study drug and ending with the last unformed stool passed
- Proportion of patients with clinical failure defined as failure to achieve formed stool within \leq 3 days (72 hours) of the start of treatment with the study drug or clinical deterioration or worsening of symptoms by Study Day 5 (\pm 1 day)
- Proportion of patients with improvement of diarrheal syndrome, defined as reduction of \geq 50% in the number of unformed stools (soft or watery) passed during the intervals 0-24 hours, 24-48 hours, 48-72 hours, 72-96 hours, and 96-120 hours after the first dose of study drug, compared to the number of unformed stools passed during the 24 hours immediately preceding first dose of study drug
- The number of unformed stools (soft or watery) passed during the intervals 0-24 hours, 24-48 hours, 48-72 hours, 72-96 hours, and 96-120 hours after the first dose of study drug
- The presence or absence and severity of signs and symptoms of enteric infection (abdominal pain/cramps, excessive gas/flatulence, nausea, vomiting, fecal urgency, tenesmus) – the proportion of patients with signs and symptoms of enteric infection during the intervals 0-24 hours, 24-48 hours, 48-72 hours, 72-96 hours, and 96-120 hours after the first dose of study drug
- Microbiological cure defined as a post-treatment culture that was negative for the pre-treatment etiologic pathogen.

4.3 Safety endpoints

The safety endpoints in this study are:

1. Incidence of reported adverse events (AEs)
2. Changes in vital signs and clinical laboratory parameters

5 SAMPLE SIZE AND POWER

According to the FDA Draft Guidance on rifaximin³ sample sizes should be chosen such that the power is sufficient to establish therapeutic equivalence between generic and RLD rifaximin (Xifaxan) and sufficient to show that both are active compared to placebo (study sensitivity). Therapeutic equivalence is to be shown for the PP (per protocol) population whereas study sensitivity is to be shown for the modified Intent to Treat (mITT) population.

A sample size of 135 in the generic Rifaximin and 135 in the Xifaxan treatment groups achieve approximately [REDACTED] power to detect therapeutic equivalence when the margin of equivalence, given in terms of the difference, extends from -0.20 to 0.20. The calculations assume that:

- two one-sided Z tests (pooled) at the 0.05 significance level are used (corresponding to a 90% CI for the difference of success proportions);

- [REDACTED]
- [REDACTED]

Concerning the assessment of study sensitivity, a sample size of 170 in the generic Rifaximin group and Xifaxan® group and 85 in the Placebo group achieve approximately [REDACTED] power to detect a difference between the group proportions of [REDACTED], assuming that:

- [REDACTED]
- two-sided Z tests (pooled) at the 0.05 level will be used.

Patients will be randomized 2:2:1 to generic Rifaximin (n=180), Xifaxan (n=180), and Placebo (n=90). A total of 450 patients will be randomized. As it can be anticipated that no more than 5% of patients will be excluded from the mITT population, and no more than 20% of patients from the mITT population will be excluded from the PP population this sample size will have sufficient power to show therapeutic equivalence and study sensitivity.

6 ANALYSIS POPULATIONS

6.1 Safety Population

The Safety population includes all randomized patients who received at least 1 dose of the study product. In this population, treatment will be assigned based upon the treatment patients actually receive regardless of the treatment to which they were randomized. The safety population will be used for safety analyses.

7 STATISTICAL CONSIDERATIONS AND ANALYSIS

7.1 Derived Variables

The below table provide the list of derived variables for duration derivations, drug compliance, baseline derivations and other important derivations applicable for this study.

Variables	Formula
Derivation of Duration	
Study day	Study days will be based on the day and time of first administration of study drug which is Day 1. Subsequent study days will be calculated as 24 hours interval from the first dose.
Duration of Study Drug (hours)	The date/time of last dose – date/time of first dose rounded to hours
Drug Compliance	
Compliance	(Number of tablets taken)/ (Number of scheduled tablets) x 100 For a patient that drops out early, the number of scheduled tablets should be the number the patient should have taken till the time subject dropped out.
Baseline Derivations	
Baseline	Baseline is defined as the last non-missing assessment prior to start of the first study drug administration.
Change from baseline	Post baseline value – Baseline
Percent change from baseline	$[(\text{Post baseline value} - \text{Baseline})/\text{Baseline}] * 100$

7.2 Definitions

7.2.1 Definitions relative to safety criteria/AEs

7.2.1.1 Adverse Event (AE)

An adverse event/experience (AE) is any untoward medical occurrence in a patient or clinical investigation patient administered a pharmaceutical product and which does not necessarily have to have a causal relationship with this treatment.

An AE can therefore be any unfavorable and unintended sign (including an abnormal laboratory finding, for example), symptom, or disease temporally associated with the use

of a medicinal product, whether or not considered related to the medicinal product.

7.2.1.2 Serious Adverse Event (SAE)

A SAE is any AE that:

- results in death
- is life-threatening
- results in persistent or significant disability/incapacity
- is a congenial anomaly/birth defect
- requires inpatient hospitalization or prolongation of existing inpatient hospitalization
- is medically significant: medical and scientific judgment should be exercised in deciding whether expedited reporting is appropriate in other situations, such as important medical events that may not be immediately life-threatening or result in death or hospitalization but may jeopardize the patient or may require intervention to prevent one of the other outcomes listed above. These should also usually be considered serious.

Whether AE is serious and the seriousness criteria met will be collected on eCRF.

7.2.1.3 Pre-treatment AEs, Treatment-emergent AEs

- An AE is defined as pre-treatment if its onset date/time is before the date/time of the first intake of study medication
- An AE is defined as treatment-emergent if its onset date/time is on or after the date/time of the first intake of study medication or if a pre-existing condition becomes worse after the date/time of first intake of study drug.

7.2.1.4 Treatment-related AEs

Relationship of AE with study drug is recorded on eCRF page with options “Suspected”, “Not Suspected”, and “Not Applicable”. Any AE with “Suspected” relationship to the study drug will be considered as treatment-related.

7.3 Handling of missing data and outliers

Missing safety data will not be imputed and will be presented as observed.

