12.1.3 Relationship to the Investigational Product

Assessment of AEs will be made by the Investigator after having evaluated all accessible data and, if necessary, re-evaluation of the case as new information becomes available. Investigational product includes the test product under evaluation and the reference product or placebo that is given during any phase of the study.

The Investigator will make a judgment considering whether or not, in his/her opinion, the AE was related to the drug according to the following classification:

Suspected:	The temporal relationship of the clinical event to study treatment administration makes a causal relationship possible , and other drugs, therapeutic interventions or underlying conditions do not provide a sufficient explanation for the observed event.
Not suspected:	The temporal relationship of the clinical event to study treatment administration makes a causal relationship unlikely , or other drugs, therapeutic interventions or underlying conditions provide a sufficient explanation for the observed event.

Causality assessments are critical and must be provided for each unique event reported and for each study treatment or concomitant medication, if applicable. Missing causality assessments will be handled by the Sponsor as “suspected” to study treatment.

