12.1.4 Adverse Events Documentation

Any AE (non-serious and serious) occurring after the patient has provided study-specific informed consent until the last study visit of the patient has to be recorded on the AE pages of the eCRF. The following information is to be recorded:

- verbatim/AE description
- time and date for AE start and stop
- maximum intensity
- seriousness
- causality rating
- action taken to treat AE
- action taken with study drug

- whether or not the AE caused the patient to discontinue
- outcome.

The occurrence of AEs should be sought by non-directive questioning of the patient at each visit during the study. AEs also may be detected when they are volunteered by the patient during or between visits or through physical examination, laboratory test or other assessments. All AEs should be treated appropriately. Treatment may include one or more of the following: no action taken (i.e. further observation only); study drug dosage adjusted/temporarily interrupted; study drug permanently discontinued due to this AE; concomitant medication given; non-drug therapy given, patient hospitalized/patient's hospitalization prolonged. The action taken to treat the AE should be documented in the eCRF. In addition, the action taken with the study drug should be documented and be assigned to one of the following categories: not changed, withdrawn, reduced, increased, interrupted, unknown and not applicable. Concomitant medication, other treatments or changes in the administration of the study drug should be defined and be also documented.

Medical conditions/diseases present before starting study drug are only considered AEs if they worsen after enrolment. Abnormal laboratory values or test results constitute AEs only if they induce clinical signs or symptoms, are considered clinically significant, or require therapy.

Once an AE is detected, it should be followed until its resolution or until it is judged to be permanent. The outcome should be documented and be assigned to one of the following categories: not recovered/unchanged, condition deteriorating, recovered/resolved, improving/recovering, recovered/resolved with sequelae, fatal or unknown. The assessment of an AE should be made at each visit (or more frequently, if necessary) of any changes in severity, the suspected relationship with the investigational product, the interventions required to treat it, and the outcome.

AE/SAE between informed consent and first dosing

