12.1.8 Reconciliation

Reconciliation between the safety database of the Sponsor and the clinical database at the CRO will be done periodically as described in a reconciliation plan by comparing line listings from the safety database with the data in the clinical database.

The data management will review the eCRFs/clinical database for potentially unreported SAEs or other individual safety cases. For any Individual Safety Case Report, the following parameters need to match exactly between the clinical and the safety database: trial number, site number, patient number, randomization number (if applicable), investigational drug, seriousness, date of death (if applicable) and Investigator causality. All other parameters only need to be plausibly and medically consistent. For any SAE assessed as suspected, a more detailed reconciliation should be conducted, including treatment dates and medical history.

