16.2 Study Monitoring

The Investigator shall permit the Site Monitor to review study data as frequently as deemed necessary to ensure that data are being recorded in an adequate manner and that protocol adherence is satisfactory.

The Investigator shall access medical records for the Monitor in order that entries in the eCRF may be verified. The Investigator, as part of his/her responsibilities, is expected to cooperate with ██████ in ensuring that the study adheres to GCP requirements.

Monitors will perform 100% source data verification to confirm that the data recorded in the eCRF reported data are accurate, complete and verifiable from the medical/study records of each patient; the presence of appropriately signed and dated ICF; adherence to inclusion/exclusion criteria; and documentation of all SAEs.

The Investigator may not recruit patients into the study until such time that a visit, or with the agreement of the Sponsor, attendance at the Investigator meeting, has been made by a Sponsor/██████ monitor to conduct a detailed review of the protocol and eCRF.

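### SAP 7.3 makes no exception for missing causality, so a TEAE still blank at database lock may be left out of treatment-related outputs although protocol 12.1.3 would include it

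*SAP*

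**What the plan says.** **Protocol.** Section 12.1.3 requires a judgement for every event ("Causality assessments are critical and must be provided for each unique event reported") and then provides for the case where none is given: "Missing causality assessments will be handled by the Sponsor as" 'suspected'. It names the Sponsor as the party that acts. It does not say whether this is done in the safety database, in the clinical database or at analysis. The AE analysis section, 13.2.7.1, has no rule for missing causality.

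**SAP.** Section 7.2.1.4 gives three eCRF options ('Suspected', 'Not Suspected', 'Not Applicable') and says that any AE with a 'Suspected' "relationship to the study drug will be considered as treatment-related". Section 7.3 reads "Missing safety data will not be imputed and will be presented as observed", and 7.3.1 on missing-data methods is marked not applicable. Section 8.6.1 has a rule for several AEs within one system organ class (SOC) or preferred term (PT), but nothing on a blank causality. Section 9 lists one change from the protocol, the removal of the efficacy analyses.

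**The concern.** The two documents give different results for the same event. Under protocol 12.1.3 a blank counts as 'suspected'. Under the SAP as written it stays blank, does not meet the definition in 7.2.1.4, and is not treatment-related. The protocol rule is the conservative one, and the SAP text that will drive programming does not carry it.

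With efficacy dropped, the final analysis is safety only, so the AE tables are a main part of what will be reported. At stake is the number of related TEAEs, and of patients with one, by treatment group.

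**Working it through.** The plan gives no figure to reproduce. The check is to follow one blank event through the text, count the outputs it touches, and work out how far one patient can move a rate.

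**1. Path of a TEAE with causality blank at lock**
- SAP 7.3: not imputed, so it remains blank.
- SAP 7.2.1.4: not 'Suspected', so not treatment-related.
- Protocol 12.1.3: handled as 'suspected', so related.
- SAP section 9: no departure declared.

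The rules agree only if the blank has been replaced before lock. Neither document says that it will be. SAP section 1 says only that analysis follows once "the resulting clinical database has been cleaned, quality-checked and locked".

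**2. Outputs affected (SAP 8.6.1)**
- Nine tables are listed. Three rest wholly on relatedness: related TEAEs, related serious TEAEs, and related TEAEs by maximum severity.
- The overall summary has six lines (any TEAE, serious, severe, related, leading to discontinuation, death), of which one uses relatedness. That makes 3 + 1 = 4 of 9 tables touched.
- Six listings are named, of which one (related TEAEs) uses relatedness.

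**3. Shift in an arm's overall related-TEAE rate**

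Let k be the number of patients in an arm who have a blank-causality TEAE and no other 'Suspected' TEAE in any SOC or PT. Let n be the number treated in that arm. The SAP rate is below the protocol-rule rate by 100 × k/n percentage points.
- k = 0: shift 0.
- k = 1, n = 180 (planned for each active arm, SAP section 5): 100/180 = 0.56 points.
- k = 1, n = 90 (planned for placebo, SAP section 5): 100/90 = 1.11 points.

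SAP section 9 reports a low number of randomized patients, so the shift per patient will be larger than these planned-size values. The actual n per arm is not in the documents.

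**4. Tables that can change even when k = 0**

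Having another 'Suspected' AE in the same SOC or PT does not protect every table.
- *Related serious TEAEs:* a patient has a 'Suspected' non-serious AE and a blank serious AE of the same PT. The SAP omits the patient from this table; the protocol rule adds an entry.
- *Related TEAEs by maximum severity:* a patient has a 'Suspected' mild AE and a blank severe AE of the same PT. The SAP shows mild; the protocol rule shows severe.

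In both cases the SAP omits an event that the protocol rule would count. In the second, the omission appears as a lower severity grade.

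**The case against.** The best reply has three parts.

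**The texts can be read together.** SAP 7.2.1.4 does not say that an event is related *only* if the site recorded 'Suspected'. Once the Sponsor has handled a blank as 'suspected', the event meets the SAP definition. Protocol 13.2 says deviations from its planned analysis will be described in the SAP, and section 9 declares none on this point. Protocol 12.1.3 also sits in the safety-assessment chapter and may be a case-handling convention rather than an analysis rule. The step that applies it could be in the reconciliation plan or the table templates, which are separate documents.

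**Blanks should be rare.** Protocol 12.1.4 lists "causality rating" among the items to record for every AE. Section 16.2 states "Monitors will perform 100% source data verification", and the data are cleaned before lock. Section 12.1.8 adds a further check: "For any Individual Safety Case Report, the following parameters need to match exactly between the clinical and the safety database", and Investigator causality is one of those parameters.

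**Nothing is hidden.** The event stays in the all-TEAE tables and listings, where the blank would be visible. SAP 8.6 plans no statistical test.

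Much of this stands. A reader might infer that the SAP overrides the protocol on purpose, or that related events will be under-reported. The documents support neither: filling blanks before lock would remove the conflict, and whether any will remain is unknown. Nor does every blank move an arm's rate, since that requires the condition on k above.

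The reply does not supply the missing statement. Neither document places the 12.1.3 default at any step. Source verification checks entries against source and cannot supply a judgement that was never made. The reconciliation in 12.1.8 is stated for Individual Safety Case Reports, not for every non-serious AE, so a leftover blank is most plausible for a non-serious TEAE. The protocol itself foresees blanks by writing a rule for them.

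**Conclusion.** The point holds as a conditional inconsistency of minor weight. If a TEAE's causality is still blank at lock, the SAP as written leaves the event out of three tables, one summary line and one listing in which protocol 12.1.3 would include it. Relative to that rule, the error can only under-count related TEAEs.

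The size is unknown and may be zero, because the documents give neither the number of blanks nor the number treated per arm. The per-patient values at planned enrolment are illustrations, not estimates of what will occur. A reader might take the low enrolment to mean that the distortion is large. It makes each affected patient count for more, but says nothing about how many there are.

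The conclusion assumes that 12.1.3 is meant to govern the reported counts and that blanks are not filled before lock. If either assumption fails, no count is wrong and only the wording needs clarifying.

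**What to change.** Keep the sentence in SAP 7.3 and add an exception: a TEAE with missing causality is counted as 'Suspected' (protocol 12.1.3). Cross-reference this in 7.2.1.4, show the observed blank in the listings, and report the number of such events by treatment group.

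An equivalent remedy is to state in the SAP that the 12.1.3 default is applied in the clinical database before lock.

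The first option costs one clause, one cross-reference and one count line by treatment group; the second costs one sentence. If no causality is blank at lock, no related-AE count changes under either.
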